4.4 Clinic-Level Data Collection

The following data will be collected in the clinic. All data will be entered by site personnel using an electronic data capture (EDC) system. Access to the EDC system, IBM Clinical Development, employed for collection of the patient data will be controlled centrally by the DCRI through distribution of EDC study specific access codes. DCRI data export services establishes regular exports of the data to be stored on the DCRI server.

Baseline

• Geographic classification: Urban vs non-urban will be collected by the DCRI study team prior to site activation.

12 Months or End of Study (intervention sites only)

A provider survey to be completed by the site investigator will be conducted to collect the following information:

- Acceptability of educational intervention
- Appropriateness of educational intervention

	Baseline	3 months	6 months	9 months	12 months
Required contact w/ patient	 Informed Consent SSN # (unless patient opts out) Medications of interest, as reported by the patient 	Telephone (or visit if done as SOC between 2-4 months after enrollment) 1) Vital Status 2) Medications of interest, as reported by the patient	Telephone (or visit if done as SOC between 5-7 months after enrollment) 1) Vital status 2) Medications of interest, as reported by the patient 3) Clinical events assessment as reported by the patient	Telephone (or visit if done as SOC between 8- 10 months after enrollment) 1) Vital Status 2) Medications of interest, as reported by the patient	Telephone (or visit if done as SOC between 11- 13 months after enrollment) 1) Vital Status 2) Medications of interest, as reported by the patient 3) Clinical events assessment as reported by the patient
Required health record check	 Demographics (age, sex, race) Baseline visit vital signs (sBP, dBP, BMI) Most recent lab values (HbA1c, LDL-C, BMP) Medications of interest prescribed, as collected from health record 	1) Medications of interest prescribed, as collected from health record	 Medications of interest prescribed, as collected from health record Clinical events assessment, as collected from health record 	1) Medications of interest prescribed, as collected from health record	 Most recent vital signs (sBP, dBP, BMI), as collected from the health record Most recent lab values (HbA1c, LDL-C, BMP), as collected from the health record Medications prescribed, as collected from the health record Clinical events assessment, as collected from health record

 Table 3. Patient-Level Data Collection by the Site for Both Arms (gray shade denotes data that will be assessed in the intense education intervention arm only)

In addition to the above data collected by sites, the DCRI coordinating center may assess allcause mortality by using patient social security numbers to access the National Death Index. Vital status may be assessed for all patients who have provided SSN at up to 5 years after last patient follow-up visit.

5. Independent External Review Committee

This committee will be an independent body that will provide critical, independent, and unbiased review of all components of the trial during the design, conduct, and dissemination phases. The committee will be responsible to assure the trial is being conducted in a way to assure patient

safety and thus will periodically review safety and clinical outcome data. This committee is analogous to a Data and Monitoring Committee to ensure protection of human participants. The committee may consist of 2 experts who meet several times over the course of the project and who will assess data. The data will be provided to the Independent External Review Committee via summary reports compiled by a statistician and programmer. After review of the data, they will make recommendations to the steering committee if trial modification is needed to assure patient safety or improve trial integrity. A charter for this committee will be developed prior to start of study.

6. Safety Management and Reporting of Adverse Events/Serious Adverse Events

6.1 Definition of Adverse Events

Adverse event

An adverse event (AE) is defined as any untoward medical occurrence in a patient or clinical investigation participant administered a medicinal product and which does not necessarily have a causal relationship with this treatment. An AE can therefore be any unfavorable and unintended sign (e.g. an abnormal laboratory finding), symptom, or disease temporally associated with the use of a medicinal product, whether or not considered related to the medicinal product.

Adverse drug reaction (ADR)

An adverse drug reaction is defined as a response to a medicinal product which is noxious and unintended. Response in this context means that a causal relationship between a medicinal product and an adverse event is at least a reasonable possibility. Adverse drug reactions may arise from use of the product within or outside the terms of the marketing authorization or from occupational exposure. Conditions of use outside the marketing authorization include off-label use, overdose, misuse, abuse and medication errors.

Serious adverse event

A serious adverse event is defined as any AE which

- results in death
- is life-threatening
- requires in-patient hospitalization or prolongation of existing hospitalization
- results in persistent or significant disability or incapacity or is a congenital anomaly/birth defect

Life-threatening in this context refers to a reaction in which the patient was at risk of death at the time of the reaction; it does not refer to a reaction that hypothetically might have caused death if more severe.

Medical and scientific judgment should be exercised in deciding whether other situations should be considered serious reactions, such as important medical events that might not be immediately life threatening or result in death or hospitalization but might jeopardize the patient or might require intervention to prevent one of the other outcomes listed above. Examples of such events are intensive treatment in an emergency room or at home for allergic bronchospasm, blood dyscrasias or convulsions that do not result in hospitalization or development of dependency or abuse. Any suspected transmission via a medicinal product of an infectious agent is also considered a serious adverse reaction.

6.2 Adverse Event and Serious Adverse Event Collection and Reporting

If an adverse drug event is reported by the patient participant during the COORDINATE-Diabetes study, the patient participant will be instructed to contact his or her study physician. The study physician is responsible for reporting via MedWatch, the FDA Safety Information and Adverse Event Reporting Program. The site Primary Investigator will be responsible for safety reporting AEs which occur during the conduct of the study to the competent regulatory authorities, accredited Institutional Review Boards and/or Independent Ethics Committee(s) (IRB/IEC(s)) in accordance with the applicable laws and regulations.

Adverse event reporting to Boehringer-Ingelheim (BI)

Each site shall report

- (i) all ADRs (serious and non-serious)
- (ii) all AEs with fatal outcome
- (iii) pregnancies in female participants and partners of male participants

that are associated with the **BI Drugs administered for the disease in scope of the study (e.g., empagliflozin, linagliptin and its combinations** by fax to the BI Unique Entry Point using BI NIS SAE report form in following timelines.

BI Unique Entry Point:

Boehringer-Ingelheim Pharmaceuticals, Inc. [contact]

All serious ADRs and AEs with fatal outcome shall be forwarded immediately (within 24 hours or next business day whichever is shorter).

All non-serious ADRs and Pregnancy Monitoring Forms shall be forwarded within7 days.

The investigator carefully assesses whether an AE constitutes an ADR using the information below.

DCRI is responsible for training the sites regarding the safety reporting to BI based on the agreement, protocol and BI training material.

Causal relationship of adverse event

The definition of an adverse reaction implies at least a reasonable possibility of a causal relationship between a suspected medicinal product and an adverse event. An adverse reaction, in contrast to an adverse event, is characterized by the fact that a causal relationship between a medicinal product and an occurrence is suspected.

Medical judgment should be used to determine the relationship, considering all relevant factors, including pattern of reaction, temporal relationship, de-challenge or re-challenge, confounding factors such as concomitant medication, concomitant diseases and relevant history.

Causality should be assessed for each event as either "yes" or "no." No other variation should be reported.

Intensity of adverse event

The intensity of the AE should be judged based on the following:

Mild: Awareness of sign(s) or symptom(s) which is/are easily tolerated

Moderate: Enough discomfort to cause interference with usual activity

Severe: Incapacitating or causing inability to work or to perform usual activities

The intensity of adverse events should be classified and recorded according to the CTCAE

Criteria in the NIS SAE form.

Pregnancy

In rare cases, pregnancy might occur in a study. Once a participant has been enrolled into the study, after having taken BI Drug administered for the disease in scope of the study, the investigator must report any drug exposure during pregnancy, which occurred in a female subject or in a partner to a male subject to the Sponsor by means of BI Pregnancy Monitoring Form provided.

Reporting of related adverse events associated with any other BI drug

The investigator is encouraged to report all adverse events related to any BI drug other than BI Drugs used for the disease in scope of the study according to the local regulatory requirements for spontaneous AE reporting at the investigator's discretion by using the locally established routes and AE report forms. The term AE includes drug exposure during pregnancy and, regardless of whether an AE occurred or not, any abuse, off-label use, misuse, medication error, occupational exposure, lack of effect, and unexpected benefit.

7. Statistical Hypotheses, Randomization, and Sample Size Determination

7.1 Hypothesis

The trial hypothesis is that the primary outcome (proportion of patients achieving guidelinerecommended management for T2DM and CVD at 12 months, as initiated or confirmed by a cardiologist, with a composite score of 3) will be higher in the intensive educational intervention arm than in the basic education arm.

The null hypothesis is that the proportion of patients achieving guideline-recommended management for T2DM and CVD at the last follow-up visit, as initiated or confirmed by a cardiologist, with a composite score of 3 will be similar between the intensive intervention educational arm and basic education arm.

7.2 Randomization

Site randomization: Site will be randomized when eligibility to participate in the trial has been established. To minimize imbalance between population characteristics in the basic education and intensive educational intervention groups, a stratified randomization based on geographic classification (urban or non-urban) will be implemented to ensure that selected site characteristics are balanced within each stratum. Site randomization will be conducted through a database platform using the randomization scheme (block randomization based on stratification factors) generated by the study statistician and uploaded by data management. Site management has a "button" on their web portal that they can select when a site is ready to be randomized (must have IRB approval and contract executed). Randomized site will receive an official email with their randomization status/assignment.

Mitigation of potential sample bias after site randomization

CONFIDENTIAL

The following processes will be implemented:

- Education before randomization, after randomization, and throughout the enrollment process that sites should AVOID enrolling only a certain type of patient (i.e., either high-or low-risk only)
- Assessment of patient enrollment characteristics once 25% and 50% of patients have been enrolled in the trial overall and by site to ensure that baseline characteristics are similar in the basic education arm and intensive educational intervention arm. If an imbalance is observed, measures will be taken to visit the involved sites and remedy the issue with the on-site clinical leads.
- Outcomes will be adjusted for differences in baseline characteristics, to be detailed in the statistical analysis plan.

7.3 Sample Size Determination

The primary outcome is the proportion of patients receiving guideline-recommended therapy, defined as a composite score of 3 at the last follow-up visit. The primary analysis is based on the comparison of primary outcome between the basic education and intensive educational intervention arms. The sample size provides adequate power to detect a clinically meaningful effect size of at least a 10% difference between treatment arms in the proportions of patients achieving a composite score of 3 by the last follow-up visit.

In this cluster-randomized trial, where the experimental unit is site, the effective sample size and power is impacted by intra-cluster correlation (ICC). For the primary outcome, the sample size calculation is based on the ability to detect at least a 10% difference between treatment arms in the proportion of patients achieving guideline-recommended management for T2DM and CVD with composite score of 3. The effect size of a 10% change has been chosen as a clinically meaningful difference between the intensive educational intervention and basic education arms.

A minimum of 42 sites ("clusters") with an average cluster size of 25 patients per site (a total of 1050 patients) will provide at least 85% power to detect a 10% difference in the primary outcome between educational intervention arms through the last follow-up visit (6 to 12 months). This estimate of a minimum of 21 sites per arm (average of 25 patients per site) is based on the assumption of 10% of patients in the basic education arm, and at least 20% in the intensive educational intervention arm, receiving guideline-recommended therapy at the last follow-up visit, with an intra-correlation coefficient (ICC) of 0.05, and two-sided type I error rate of 0.05. The sample size/power calculations were carried-out using R function "n4props" in (package "CRT Size").¹¹

7.4 Planned Statistical Analysis

An initial SAP defining the analysis populations, known covariates of interest, and procedures for handling missing and spurious data will be established and archived prior to enrollment of the first patient. The full statistical analysis plan (SAP) will be finalized before database lock. This section is a summary of the planned statistical analyses of the primary and secondary outcome.

The primary outcome will be analyzed using a multivariable logistic regression model with a generalized estimating equations (GEE) using a compound symmetry working correlation matrix to account for the effect of clustering, as well as adjustment for potential baseline factors as

covariates (including the baseline composite score). This model will provide the estimated adjusted odds ratio and 95% CI.

For time-to-event outcomes, multivariable Cox proportional hazards models with shared frailties to account for clustering effects will be used. Adjusted hazard ratio and 95% CI will be estimated from the Cox model after adjustment for pre-specified baseline factors. The complete list of pre-specified adjustment variables will be described in the final study SAP.

Baseline comparisons of participant characteristics in each arm will be summarized as the mean (SD), median (25th, 75th percentiles) for continuous variables, and as counts (percentages) for categorical variables. Differences in baseline participant characteristics between randomized arms will be compared using a Wilcoxon rank-sum test for continuous variables and the Pearson's chi-square test or the Fisher's exact test for categorical variables. All trial objectives will be analyzed using the intention-to-treat principle.

The primary database lock is planned after the last patient enrolled has completed 6 months of follow-up. Patient death will be reported to BI as an adverse event if the patient was identified to be on a BI drug for the disease in focus of the study.

8. Electronic Health Record Study Plan

In addition to the educational interventional trial, an observational analysis will be conducted in tandem with a subset of sites with existing datamarts containing EHR data in a common data model (CDM) format. The objectives of this observational analysis are to describe the clinical characteristics, management, and outcomes of patients with T2DM and CVD in current practice across an array of health systems in the United States and to characterize trends in the quality of care for patients with T2DM and CVD over time.

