3.2.3 Clinical time-to-event outcomes

A secondary important objective of this trial is to assess whether the intervention will be associated with decreased clinical outcomes with 12-months. The endpoint of interest would be the composite of all-cause death; hospitalization for: MI, stroke, decompensated heart failure, or urgent revascularization (coronary, peripheral, carotid). This endpoint will be measured in days from enrollment date to event date for those patients with an event; otherwise to time of last contact date for those patients without an event, ie censored. Each of the clinical time-to-first event outcomes will also be summarized individually with no formal statistical testing, ie will be

presented as hazard ratios (HRs) and 95% CIs. Estimates of the event rates by study arms will be displayed graphically using Kaplan-Meier cumulative risk⁴. Cox proportional hazards model with shared frailty⁵ (ref) to account for clustering effect will be used to estimate unadjusted HR (95% CI). The primary analysis will be a multivariable Cox proportional hazards model with shared frailty to account for clustering effect, adjustment for pre-specified baseline factors (see Appendix 1, Section 8.1 for list).

4. Tertiary Endpoints

All-cause mortality, as assessed by vital status obtained through the National Death Index or other sources will be assessed at 2 and 5 years after the final visit. Patient death will be reported to Boehringer Ingelheim (BI) as an adverse event if the patient was known to be on BI medication for the treatment of T2DM.

5. Implementation Endpoints

At 12 months from site randomization, a provider survey to be completed by the site investigator will be conducted to collect the following information:

- Acceptability of educational intervention
- Appropriateness of educational intervention

Provider survey data will be summarized as the mean (SD), median (25th, 75th percentiles) for continuous variables, and as counts (percentages) for categorical variables by intervention arm. Depending on the primary results and site variation in implementation, we may explore the association between site implementation and the primary outcome.

6. Electronic Health Record Sub-study

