A subset of sites with existing datamarts containing EHR data will be included in an observational analysis to describe the clinical characteristics, management, and outcomes of patients with T2DM and CVD in current practice across an array of health systems and to characterize trends in the quality of care for patients with T2DM and CVD over time. These data will not be used to assess the effect of the intervention. A detailed description of the EHR sub-study endpoints and analysis will be contained in a separate statistical analysis plan.

7. Subgroup Analysis

The primary outcome will be assessed for the subgroups using the same methods as the primary analysis. Results of the subgroup analysis will be presented graphically with a forest plot. We will assess the following subgroups:

Subgroups:

- Age: Age ≥ 65 and age < 65
- Sex: Males and females
- Race: White, Black, and Asian/Other
- LVEF ≥ 40 and LVEF < 40
- History of heart failure and no history of heart failure
- History of atrial fibrillation and no history of atrial fibrillation

8. References

1. Team RC. R: A language and environment for statistical computing. 2013
5. Austin PC. A Tutorial on Multilevel Survival Analysis: Methods, Models and Applications. *Int Stat Rev*. 2017 August ; 85(2): 185–203.

9. Appendix 1: Covariates of Interest

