9.1 Potential Adjustment Variables for Primary Outcome Model

Variable	Variable Type
Intervention	yes/no
Site: Urban vs. non-urban	yes/no
Age	continuous
Male sex	yes/no
Race	categorical (Black, Asian/Other, vs. White)
Baseline composite score	ordinal (0-2)

Charlson Comorbidity Index (CCI)	categorical (severe defined as CCI scores ≥ 5 , moderate defined as CCI scores of 3–4, vs. mild defined as CCI scores of 1–2)
Baseline systolic BP	continuous
Baseline diastolic BP	continuous

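### The Cox models for clinical events borrow the prescribing outcome's covariate list, which does not name heart failure history, so an enrolment imbalance in it may remain in part in the adjusted hazard ratio

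*Protocol*

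**What the plan says.** Protocol 7.4 plans shared-frailty Cox models for time-to-event outcomes: "Adjusted hazard ratio and 95% CI will be estimated from the Cox model after adjustment for pre-specified baseline factors". It leaves the list of variables to the SAP.

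Protocol 7.2 recognises that patients are selected after clinics know their arm. It names three safeguards: education of sites, checks of enrolled patients' characteristics at 25% and 50% of enrolment, and adjustment: "Outcomes will be adjusted for differences in baseline characteristics, to be detailed in the statistical analysis plan".

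SAP 3.2.3 makes the adjusted model the main analysis of the clinical composite, which is death from any cause or a hospital stay for MI, stroke, decompensated heart failure or urgent revascularization. Its covariates come by cross-reference: "adjustment for pre-specified baseline factors (see Appendix 1, Section 8.1 for list". Section 8 of the SAP is the reference list. The list that fits is headed "9.1 Potential Adjustment Variables for Primary Outcome Model". It contains intervention, urban site, age, sex, race, baseline composite score, Charlson index in three classes, and systolic and diastolic blood pressure.

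Heart failure history is not in it. SAP section 7 has the subgroup "History of heart failure and no history of heart failure", and the Table 1 shell in Appendix 2 has a heart failure row. For kidney function, that shell has an eGFR row and Protocol 4.4, Table 3 collects "Most recent lab values (HbA1c, LDL-C, BMP" at baseline.

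**The concern.** The list was drawn up for whether patients are prescribed guideline therapy. What predicts prescribing need not predict death or hospitalization. Heart failure history is the baseline state of one component of the composite, yet it enters the Cox model only through whatever the Charlson classes capture.

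Elsewhere the SAP tailors its covariates to the outcome. Continuous intermediate outcomes adjust for their own baseline value (3.2.2). Binary ones have a separate list, 9.2, which includes whether the target was met at baseline. The clinical-event models get no such treatment.

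At stake is the reading of the adjusted hazard ratio. An arm that happened to enrol more patients with heart failure would look somewhat worse than it is, and the other arm somewhat better. Of the three safeguards in Protocol 7.2, adjustment is the only one that acts on patients already enrolled.

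**Working it through.** **1. The plan's own figure.** Protocol 7.3 states that 42 sites of 25 patients "will provide at least 85% power to detect a 10% difference in the primary outcome", with rates of 10% and 20%, ICC 0.05 and a "two-sided type I error rate of 0.05".
- Design effect: 1 + (25 − 1) × 0.05 = 2.2.
- Effective n per arm: 525 / 2.2 = 238.6.
- z = 0.10 / √[(0.09 + 0.16) / 238.6] = 3.09. Power = Φ(3.09 − 1.96) = 0.87, or 0.854 with a t reference on 40 df.

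The figure reproduces, but it concerns prescribing only. The documents give no event rate, event count or detectable hazard ratio for clinical events, so every prevalence, prognostic hazard ratio and event count below is an assumption.

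**2. Size of the bias before Charlson adjustment.** With no true effect, prevalence p1 and p0 of heart failure history in the two arms and prognostic hazard ratio h, the spurious hazard ratio is about [1 + p1(h − 1)] / [1 + p0(h − 1)]. Assume overall prevalence 25%, split evenly around that value.

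| h | no imbalance | 5 points (27.5% vs 22.5%) | 10 points (30% vs 20%) |
|---|---|---|---|
| 1.5 | 1.00 | 1.1375/1.1125 = 1.02 | 1.15/1.10 = 1.05 |
| 2 | 1.00 | 1.275/1.225 = 1.04 | 1.30/1.20 = 1.08 |
| 3 | 1.00 | 1.55/1.45 = 1.07 | 1.60/1.40 = 1.14 |

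**3. How large an imbalance is plausible.** If heart failure prevalence clustered with the same ICC of 0.05 (an assumption; the protocol gives that ICC for prescribing), chance alone would give an SD of √(2 × 0.25 × 0.75 × 2.2 / 525) = 3.96 points for the difference between arms. A 5-point gap is 1.3 SD and unremarkable. A 10-point gap is 2.5 SD and would point to selection.

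**4. What the Charlson classes absorb.** The documents do not list the index's items, so two cases were simulated with a true intervention hazard ratio of 1, the SAP's three classes and no frailty term. With heart failure at 25% vs 30%, h = 2 and other risk balanced:
- Charlson scores heart failure: hazard ratio 1.027 unadjusted, 1.016 with Charlson classes, 0.990 with heart failure also in the model. Share of the bias removed by Charlson: ln(1.027/1.016) / ln(1.027/0.990) = 29%.
- Charlson does not score it: 1.035, 1.036 and 0.992. Nothing is removed.

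The standard errors of these averages are about 0.02, so the shares are rough. In simulations with kidney function imbalanced as well, the same calculation gave shares of 15% to 45% when Charlson scored one or both conditions.

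**5. Does adding the variable work, and what does it cost?** A simulation used about 11 covariates, including a three-class Charlson score that counts heart failure, with h = 3, a 10-point imbalance and about 90 events. The composite hazard ratio was about 1.13 without heart failure history and about 1.01 with it. The SD of the log hazard ratio was essentially unchanged. At about 30 events the longer model was overloaded, and one fit failed to converge.

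**6. Coefficients.** List 9.1 uses 11: race 2, Charlson 2 and one for each of the other seven variables. Heart failure history makes 12. That is 90/12 = 7.5 events per coefficient for the composite and 30/12 = 2.5 for a component with 30 events.

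**The case against.** The strongest reply is that this is a covariate preference in a secondary, unadjudicated analysis, and that the effect is small against the noise. With 90 events the standard error of the log hazard ratio is about 2/√90 = 0.211, so the 95% interval spans a factor of exp(1.96 × 0.211) = 1.51 each way. With 30 events the factor is 2.05. A spurious 1.07 at 90 events raises the two-sided error rate from 5% to about 6%, and 1.14 raises it to about 10%. Single components are presented without formal testing. Site education and the two enrolment checks may prevent an imbalance. SAP 2.1 reports standardized differences, and Table 6 shows unadjusted and adjusted estimates side by side.

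Most of this stands, and it limits the weight of the point. It does not remove it. A bias shifts the whole interval, and the SAP has no rule for acting on an imbalance that the standardized differences reveal. The loss of precision that might justify leaving the variable out did not appear for the composite. It is a fair objection for sparse components, and the fix allows for it.

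A reader might infer three stronger things that the documents do not support:
- **That the hazard ratios are biased.** No imbalance is shown. It is only made possible by open-label enrolment after randomization.
- **That the list ignores heart failure altogether.** The Charlson index, age and blood pressure are in it, and how far Charlson stands in for heart failure cannot be settled without its items.
- **That the absence of eGFR is an equal fault.** No separate figure for its effect was derived. Eligibility excludes GFR below 30, which narrows its range. Laboratory values come from standard care and are not mandated (Protocol 4.2), and SAP 2.2 fills gaps with age- and sex-specific medians.

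Nor is the sentence in Protocol 7.4 itself at fault. The gap is in SAP 3.2.3 and Appendix 1.

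**Conclusion.** The point holds in a limited form. The SAP's main model for clinical events uses a list written for a different outcome and does not name a prognostic factor that the SAP already tabulates and that is the baseline state of one component. If enrolment leaves the arms unequal in heart failure history, part of that difference may remain in the adjusted hazard ratio.

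The size is about 1.02 to 1.14 for the composite before Charlson adjustment, and somewhat less afterwards if Charlson scores heart failure. It is nil if the arms are balanced. This rests on an assumed 25% prevalence, a prognostic hazard ratio of 1.5 to 3 and an imbalance of 5 to 10 points, none of which the documents give. The primary outcome and its power are not affected. The change is worth making before database lock because it is cheap; the trial's main conclusion does not depend on it.

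**What to change.** 1. In SAP 3.2.3 and Appendix 1, give the time-to-event models their own list: the 9.1 variables plus heart failure history (yes/no), with the shared frailty kept. Use it for the adjusted composite hazard ratio in Table 6.
2. For single components with few events, pre-specify a reduced list that keeps heart failure history, for example age, heart failure history and the urban/non-urban stratification factor. With the intervention term that is 4 coefficients, or 30/4 = 7.5 events each at an assumed 30 events.
3. Baseline eGFR may be added in a sensitivity analysis only, given unmandated laboratory tests and median imputation.
4. Correct the pointer from 8.1 to 9.1. SAP 3.1, 3.2.1 and 3.2.2 also cite 8.1, and 3.2.2 cites 8.2 for the list printed as 9.2.

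The cost is a text edit and one more coefficient in the composite model. No new data are needed: the Table 1 shell and the subgroup analysis already require heart failure history, and SAP 2.2 has an imputation rule for missing medical history.
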